7.3 Exclusion Criteria

The presence of any of the following will exclude a subject from enrollment:

1. Intolerant to sorafenib/regorafenib, e.g.:
 - a. The drug is discontinued due to adverse events;
 - b. The related adverse events of Grade ≥ 2 continued/relapsed after supportive treatment and/or dose reduction or dose interruption at least 7 days;
 - c. The treatment course is less than 21 days within 28 days before discontinuation; the lowest daily dose of sorafenib is 400mg/day.
2. Medical history of hepatic encephalopathy;
3. Central nervous system metastases;
4. Treatment with molecular targeted therapies such as sorafenib, regorafenib or lenvatinib within 4 weeks before screening;
5. Treatment with locoregional HCC therapy (including but not limited to TACE, RFA), systemic chemotherapy, hormonal therapy (e.g., tamoxifen), traditional Chinese

medicine with anti-tumor effect, or clinical investigational drugs within 4 weeks prior to Screening.

6. Tested positive for both HBV and hepatitis C virus (HCV).
 - a. HCV positive is defined as anti-HCV or HCV-RNA positive
7. Life expectancy of less than 3 months.
8. Prior therapy with mTOR (TORC1 and/or TORC2) inhibitors including sirolimus, temsirolimus, everolimus and other investigational or approved mTOR/PI3K/AKT inhibitors.
9. Have received major surgery within 4 weeks before screening or plan to receive major surgery during study period;
10. Receiving active, ongoing treatment with systemic corticosteroids at a prednisone equivalent dose of ≥ 10 mg daily or other systemic immune system modulators. The exceptional cases of such criterion are listed as follows:
 - a. Intranasal, inhaled and topical steroids or local steroid injection (e.g., intra-articular injection);
 - b. Prednisone not more than 10 mg/day or its equivalent physiological dose of systemic corticosteroids;
 - c. Steroids as the prophylactic medication of allergic reactions (pretreatment before CT scan);
11. Imaging test results showing main portal venous tumor thrombus, inferior vena cava tumor thrombus or heart involvement;
12. Uncontrolled diabetes, defined as HbA1c $> 7\%$.
13. Prior organ transplant.
14. Uncontrolled pleural effusion or pericardial effusion (with clinical symptoms, fluctuation of effusion or requiring repeated drainage, oral diuretics etc.) at screening; Ascites at screening, which can be detected by physical examination, or clinical symptoms caused by ascites, or requiring special treatment such as repeated drainage, peritoneal drug perfusion etc. (subjects who only have a small amount of ascites which can be detected by imaging examination can be enrolled).
15. Persistent diarrhea or malabsorption \geq National Cancer Institute (NCI) Common Terminology Criteria for Adverse Events (CTCAE, Version 4.03) grade 2, despite medical management, or any significant gastrointestinal disorder that could affect the absorption of study drug.
16. Medical history of active upper gastrointestinal hemorrhage, ulcer or esophageal varices associated with hemorrhage or such diseases within 6 months;
17. Subjects who have medical history of human immunodeficiency virus infection and/or acquired immunodeficiency syndrome;
18. Concurrent active second malignancy for which the subject is receiving therapy, excluding non-melanomatous skin cancer, non-progressive prostate cancer treated with hormonal therapy, or carcinoma in situ of the cervix. Any cancer curatively treated >5 years prior to entry is permitted.
19. Uncontrolled intercurrent illness including, but not limited to ongoing or active infection (e.g., tuberculosis) requiring antibiotic, antifungal, or antiviral therapy (other than anti-HBV therapy), acute or chronic pancreatitis or psychiatric illness/social

situations that would limit compliance with study requirements.

20. Subjects who have clinically significant cardiovascular diseases such as Grade II and above cardiac dysfunction (New York Heart Association criteria), ischaemic heart diseases (e.g., myocardial infarction or unstable angina pectoris), clinically significant supraventricular or ventricular arrhythmia, uncontrolled hypertension (systolic blood pressure >150 mmHg and/or diastolic blood pressure >100 mmHg), echocardiography showing ejection fraction <50%, QTc interval >450 ms (male), QTc interval >470 ms (female);
21. The subject's complications or other conditions may affect protocol compliance or make the subjects unsuitable to participate in this study at the discretion of the investigator;

8. DESCRIPTION OF STUDY TREATMENTS

8.1 Description of Investigational Product(s)

Antengene Corporation will supply ATG-008 in 15 mg, 20 mg, and 30 mg tablets; ATG-008 tablets are manufactured using conventional solid oral dosage form excipients.

Study drugs are stored at room temperature at 15-25 Celsius degree.

8.2 Treatment Administration and Schedule

The first part of this study will consist of two cohorts. Six subjects will receive a single dose of 15 mg ATG-008 on Day -1 and then receive 15 mg ATG-008 daily in 28-day cycles. Providing dose-limiting toxicity (DLT) occur in less than 2 of those 6 subjects who complete Cycle 1, 24 new subjects will receive a single dose of 30 mg ATG-008 on Day-1 and then receive 30 mg ATG-008 daily in 28-day cycles. Subjects who tolerated the 15-mg dose level may then dose-escalate to 30 mg at the Investigator's discretion.

According to the previous study results, the sponsor will plan to continue to enroll approximately 40 hepatitis B virus (HBV) positive, unresectable HCC subjects who have received at least one prior line of systemic therapy. Among which, approximately 20 subjects will receive oral ATG-008 at an initial dose of 45 mg/QD and another 20 subjects will receive oral ATG-008 at an initial dose of 20 mg/BID. The pharmacokinetic (PK) samples will be collected from 10 subjects each in the two dose groups.

Each dose of study drug will be taken at the same time each day, and can be taken with or without food. On clinic visit days, study drug will be administered in the clinic after all predose tests have been completed. Subjects should come to the clinic after fasting for 6 hours and food will be taken after all fasting tests have been completed prior to dosing.

In addition to study drug, all subjects may receive best supportive care (BSC) as determined by the Investigator according to local/institutional guidelines. Best supportive care is defined as non-specific anti-tumor treatment with the effect to maximize quality of life, including antibiotics, analgesics, antiemetics, thoracentesis, pleurodesis, blood transfusions, nutritional support and excluding surgery, TACE, RFA, immunotherapy, anticancer hormonal therapy, systemic chemotherapy, and radiotherapy (Zafar, 2008).

Treatment cycles are defined for administrative purposes as 28 days (except cycle 1).

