No suspected and unexpected serious adverse reactions (SUSAR) were reported in this study. One case of DLT was observed in 15 mg dose group and no DLT in 30 mg group. The most frequently reported study drug-related TEAEs were skin rash and hyperglycemia (45.7% each), decreased appetite and pruritus (31.4% each), diarrhea and stomatitis (28.6% each), weight loss (22.9%), fatigue and platelet count decreased (20.0% each), white blood cell count decreased, mouth ulceration and proteinuria (17.1% each), nausea, hepatic dysfunction and hand-foot syndrome (14.3% each), discomfort and AST elevated (11.4% each).

As ATG-008 is firstly and orally administered hepatitis B virus (HBV) positive, HCC Asian subjects who have previously received at least one prior line of systemic therapy in this study, the overall safety profile of ATG-008 is similar to that of foreign clinical studies in Europe and America, and no unexpected new safety signal is reported, it is further confirmed that ATG-008 is well tolerated and further dose escalation is allowed.

➤ **Clinical PK: the PK profile of this study was similar to the PK profile of foreign patients in Europe and America**

The foreign study (Europe and America) CC-223-ST-001-Part A demonstrated that the unchanged ATG-008 showed linear relationship within the dose range of 7.5 mg~60 mg, and the exposure level of metabolite M1 also presented linear relationship with the dose.

The preliminary PK results of this study (ATG-008 15 mg and 30 mg) showed that the exposure level of active compound and its metabolite presented linear relationship with the dose. Compared with PK parameters of foreign studies in Europe and America, the active compound had numerically higher C_{max} and shorter T_{max} . The active compound and its metabolite had similar elimination rate (in different dose groups). Analysis of difference in PK parameters in Europe, America, and Asia showed that the difference in exposure level mainly caused by C_{max} difference, which might be related to lighter body weight and smaller volume of distribution of Asian patients.

According to the currently available data, it was estimated that the exposure level of 20 mg/BID might be lower than that of 45 mg/QD, supporting that the administration mode BID could be explored in this study. According to the above clinical efficacy, safety and PK study results, the sponsor proposed to add 2 dose groups, i.e., 45 mg/QD and 20 mg/BID (approximately 20 subjects

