1.4.1 Rationale for Dose of ATG-008

In CC-223-ST-001, frequent dose reductions, especially in 45-mg dose HCC subgroup, were

required due to mitigate toxicity: The numbers of subjects with dose reductions for subjects starting at the 30 mg and 45 mg dose levels were 12/28 (42.9%) and 18/25 (72.0%), respectively; median time to first dose reduction due to a TEAE was 43.0 days and 26.5 days, respectively.

Despite the dose reductions, encouraging signals of activity were observed in the HCC cohort including three subjects that met the criteria for radiologic PR (> 30% reduction in target lesions) at the first restaging evaluation after 2 cycles of treatment, reduction in SUV uptake by PET, and reductions in AFP. All 3 HCC subjects in phase 2 with radiologic PR were HBV+, required dose reduction to 30 mg.

Based on the high frequency of dose reductions, 45 mg daily was not considered to be an acceptable dose for further study in unresectable HCC. A dose of 30 mg daily was well tolerated in most subjects and resulted in near maximal mTOR biomarker [pAKT, pS6 and phosphorylated 4E-binding protein 1 (P4EBP1)] inhibition in blood with at least 40% to 70% inhibition of each marker. Plasma ATG-008 drug exposures at 30 mg also exceeded levels associated with mTOR biomarker inhibition and antitumor activity in preclinical tumor xenograft models. In addition, the most durable tumor response was observed in a subject with breast cancer at the 30-mg dose level during phase 1 of the study. Antengene believes these data support the selection of 30 mg QD as the most appropriate dose of ATG-008 and 15 mg QD and 30 mg QD for PK study in unresectable HCC in the study.

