4. OVERALL STUDY DESIGN

4.1 Study Design

ATG-008-HCC-001 is a MRCT trial in which ATG-008 will be administered orally in HBV+ HCC subjects who have received at least one prior line of systemic therapy in Asian countries. The trial is designed as an open-label phase 2 trial to assess PK, safety, tolerability and efficacy of oral ATG-008 administered until the appearance of radiologic disease progression (according to RECIST 1.1). The PK and safety profiles will be compared with historical ATG-008 results when

data are available.

According to the previous study results, the sponsor will plan to continue to enroll approximately 40 hepatitis B virus (HBV) positive, unresectable HCC subjects who have previously received at least one prior line of systemic therapy. Among which, approximately 20 subjects will receive oral ATG-008 at an initial dose of 45 mg/QD and another 20 subjects will receive oral ATG-008 at an initial dose of 20mg/BID. The pharmacokinetic (PK) samples will be collected from 10 subjects each in the two dose groups so as to further evaluate the PK profile of ATG-008 and its metabolites.

If the overall response rate (ORR) of tumor is greater than 15% in the study dose group (45 mg/QD or 20 mg/BID), then this study will be expanded to enroll additional approximately 110 subjects using ORR as the primary study endpoint, to further evaluate the efficacy and safety of ATG-008.

At the discretion of the Investigator, treatment may continue beyond radiologic progression until symptomatic deterioration if no other therapeutic options are available. Subjects may also receive best supportive care according to local practice. All subjects will continue to be followed after treatment discontinuation for radiologic tumor response until disease progression, death or withdrawal of consent (as defined in Section 6.4, if applicable) and new anticancer treatments until death or withdrawal of consent. Subjects will also be followed for survival until death or withdrawal of consent.

[figure not shown]
The starting dose of ATG-008 will be 15 mg daily for 28 days each cycle for the first 6 fully evaluable (including PK outcomes) subjects. Providing DLTs occur in less than 2 of 6 subjects who complete Cycle 1, additional 24 subjects will be enrolled at the starting dose of 30 mg daily. Subjects who tolerated the 15-mg dose level for at least 1 cycle may then dose-escalate to 30 mg at the Investigator's discretion.

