As of 18 Jul 2019, the preliminary clinical study data showed that this study enrolled a total of 35 HCC subjects (all were Asian, among which, 15 subjects were from Chinese mainland, 13 from Korea and 7 from Taiwan). 7 subjects received oral ATG-008 at the initial daily dose of 15 mg and 28 subjects received 30 mg). Among 35 subjects, 1 subject achieved PR, 14 subjects achieved SD, 19 subjects achieved PD and 1 subject still received the first cycle of treatment and no efficacy evaluation has been performed yet. The survivors accounts for approximately 65.7% (23/35). The diameter of the targeted lesions of tumors decreased after treatment from baseline in 38.2% (13/34) subjects. Currently, subjects who received the longest treatment had completed 11 cycles of treatment.

No suspected and unexpected serious adverse reactions (SUSAR) were reported in this study. One case of DLT was observed in 15 mg dose group and no DLT in 30 mg group. The most frequently reported study drug-related TEAEs were skin rash and hyperglycemia (45.7% each), decreased appetite and pruritus (31.4% each), diarrhea and stomatitis (28.6% each), weight loss (22.9%), fatigue and platelet count decreased (20.0% each), white blood cell count decreased, mouth ulceration and proteinuria (17.1% each), nausea, hepatic dysfunction and hand-foot syndrome (14.3% each), discomfort, and AST elevated (11.4% each).

Consequently, ATG-008 is firstly and orally administered hepatitis B virus (HBV) positive, HCC Asian subjects who have previously received at least one prior line of systemic therapy in this study, the preliminary efficacy has been observed, the overall safety profile of ATG-008 is similar to that of previous foreign clinical studies and similar drugs, and no unexpected new safety signal is reported, it is further confirmed that ATG 008 is well tolerated.

In addition, according to the results of study CC-223-ST-001-B which has been completed by Celgene, the ORR of solid tumor HCC cohort was 5.7%, among which, the best efficacy of 3 subjects (all had positive HBV) was PR and 2 of them were treated with 45 mg ATG-008 daily (the maximum tolerated dose (MTD) of ATG-008 monotherapy was 45 mg/day, the intolerable dose was 60 mg/day).

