Considering the observed preliminary efficacy and favorable safety and tolerability of ATG-008, this study proposes to continue to enroll approximately 40 subjects to receive ATG-008 at an initial dose of 45 mg/QD or 20 mg/BID (approximately 20 subjects each) to further evaluate the PK, safety, tolerability and efficacy of ATG-008.

If ORR of tumor is greater than 15% in the study dose group (45 mg/QD or 20 mg/BID), then this study will be expanded to enroll additional approximately 110 subjects using ORR as the primary study endpoint, to further evaluate the efficacy and safety of ATG-008.

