8.3 Method of Treatment Assignment

Subjects who are in the first part of this study and are enrolled into screening period will be assigned with one available subject number. The assignment to cohort of 15mg or 30mg will be in sequence.

As for approximately 40 HCC subjects who are planned to be enrolled, subjects will be randomly assigned with one available subject number during screening period to receive oral ATG-008 at an initial dose of 45 mg/QD or 20 mg/BID.

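### The 45 mg/QD and 20 mg/BID groups have no written cohort-level toxicity review, and expansion by about 110 subjects depends on ORR above 15% alone: a cheap improvement to consider

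*Combined protocol and SAP*

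**What the plan says.** **First stage.** Section 4.1 sets a rule between dose levels: "Providing DLTs occur in less than 2 of 6 subjects who complete Cycle 1, additional 24 subjects will be enrolled" at 30 mg. The same rule is in the synopsis and Sections 4.2, 6.2 and 8.2. Section 4.1 lists the DLTs as hyperglycemia, rash, fatigue and mucositis of Grade 3 or higher. Section 4.2 gives the outcome: "One case of DLT was observed in 15 mg dose group and no DLT in 30 mg group". The synopsis and Section 1.4 conclude that "it is further confirmed that ATG-008 is well tolerated and further dose escalation is allowed".

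**Second stage.** Section 8.2 plans that "approximately 20 subjects will receive oral ATG-008 at an initial dose of 45 mg/QD and another 20 subjects will receive oral ATG-008" at 20 mg/BID. Under Section 8.3, "subjects will be randomly assigned with one available subject number during screening period to receive oral ATG-008 at an initial dose" of one or the other; no staggered entry is described. Sections 4.1, 4.2, 6.2, 7.1, 8.2, 8.3 and 10.1 give these groups no toxicity review point, event count or pause. The expansion rule in Section 4.2 begins "If ORR of tumor is greater than 15% in the study dose group (45 mg/QD or 20 mg/BID"), and the consequence is about 110 more subjects. It recurs in the synopsis and Sections 4.1, 6.4.1, 7.1 and 10.1, never with a safety condition.

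**The protocol on these doses.** Section 1.4.1 says that "45 mg daily was not considered to be an acceptable dose for further study in unresectable HCC", because dose reductions were frequent, and Section 4.2 repeats that judgment. Section 1.3.2.1 says the earlier study lowered its HCC starting dose to 30 mg for the same reason. Twice-daily dosing is described only in animals (Sections 1.3.1 and 1.4.1). Section 1.4 estimates that exposure at 20 mg/BID may be below that at 45 mg/QD.

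**The concern.** The step from 15 to 30 mg had a written cohort rule. The step to 45 mg/QD, which the protocol itself calls poorly tolerated in this disease, and to a new schedule has none. The first-stage DLT results used to support the step come from 15 and 30 mg once daily, so they do not test either new regimen.

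Tolerability is part of the primary objective (Section 2.1), but no rule links it to enrollment or to expansion. Taken literally, the expansion rule would commit about 110 more subjects to a starting dose that most of the first 20 could not stay on, provided at least 4 of them responded.

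**Working it through.** **1. The plan's own figure.** Section 10.3 tests ORR of 10% against 18%, one-sided 0.025, 80% power, by the normal approximation:

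n = [(1.960·√(0.10·0.90) + 0.842·√(0.18·0.82)) / 0.08]² = 129.8, rounded up to 130. Power at 130 is 80.06%.

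The stated 130 (20+110) reproduces. A toxicity review does not enter this formula, so the fix leaves N alone.

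**2. The expansion rule.** With exactly 20 in a group, 3/20 is 15% and does not exceed it, so at least 4 responders are needed. The exact binomial chance that one group passes is 13% at a true ORR of 10%, 35% at 15% and 50% at 18%. No toxicity rate enters.

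**3. Evidence on 45 mg/QD.** Section 1.4.1 gives reductions of 18/25 = 72.0% at 45 mg (exact 95% CI 51% to 88%) and 12/28 = 42.9% at 30 mg (24% to 63%). For 30 mg and 45 mg, the "median time to first dose reduction due to a TEAE was 43.0 days and 26.5 days, respectively". The section does not say whether those medians are among reduced subjects only. If they are, half of 18, or 9 of 25 (36%), were reduced by day 26.5, close to the end of a 28-day cycle. That is about 6 × 0.36 = 2.2 of a first 6. Reductions are not DLTs, so a DLT count alone would not capture this pattern.

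**4. A count of 2 or more DLTs in the first 6.** True second-stage DLT rates are not given, so a range is assumed. P(pause) = 1 − (1−p)⁶ − 6p(1−p)⁵.

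| True DLT rate | 10% | 20% | 30% | 40% | 50% |
|---|---|---|---|---|---|
| P(pause) | 11% | 34% | 58% | 77% | 89% |

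**5. Rates taken from the documents.**

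- First-stage DLTs, 1/35 (Section 4.2): about 1%.
- Earlier study at 45 mg, 1/9 (nine subjects in Section 1.3.2; one listed DLT, rash, in Section 1.3.2.2): 14%. The exact 95% CI for 1/9 is 0.3% to 48%.
- Section 1.3.2.4 reports drug-related Grade 3 or higher hyperglycemia in 24.2% of 33 subjects. If every such event counts: 1 − 0.758⁶ − 6·0.242·0.758⁵ = 1 − 0.190 − 0.363 = 0.447, about 45%.
- The same section reports Grade 3 or higher rash in 18.2%: about 30%.

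The last two rates cover all cycles (mean 3.2 completed), so Cycle 1 rates may be lower. Even so, 24.2% of 33 is 8 subjects with Grade 3 or higher hyperglycemia, which is on the DLT list, against one DLT reported in 35. A Cycle 1 window or a controlled-by-treatment exemption could explain the difference, but Section 4.1 states neither.

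**6. A softer count.** Pausing at 4 or more of the first 10 gives 12% at a true rate of 20%, 62% at 40%, and about 21% at 24.2%.

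**The case against.** The strongest reply is that 45 mg/QD is not a new dose. It is the MTD from the earlier study, most of that study's 198 expansion subjects started on it (Section 1.3.2.2), and 25 of them had HCC. The other regimen totals 40 mg a day, with exposure estimated as possibly lower. A DLT rule at or below an established MTD is a preference on which sponsors may differ. This stands, and it lowers the urgency. It does not answer the protocol's own view that 45 mg/QD was unsuitable in HCC because of reductions.

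A reader might infer that these groups are unmonitored, or that dosing would continue whatever happened. The documents do not support that. Section 8.2.1.2 and Table 4 govern each subject's dose. Section 10.7 provides continuous reporting, including dose modifications and discontinuations. SAEs are reported within 24 hours (Sections 11.1 and 11.5), Section 4.3 plans a safety evaluation of this stage, and Section 14.8 lets the sponsor terminate. All are discretionary or subject-level, and none sets a cohort-level condition.

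A reader might also infer from 1 DLT in 35 that a 2-of-6 pause would almost never occur at first-stage tolerability. The Grade 3 or higher rates in Section 1.3.2.4 do not allow that conclusion until the DLT definition is settled. Nor does the gap between those rates and the single DLT prove undercounting, since events after Cycle 1 could explain it.

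**Conclusion.** The point holds as a cheap improvement to consider. It is a design choice, not an error in a stated figure. The visible text has no cohort-level toxicity review for either new group and no tolerability condition on expansion. The more important gap is the expansion rule, because following it literally could expand a poorly tolerated starting dose.

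The chance that a 2-of-6 pause fires rests on assumed DLT rates: 11% to 89% across 10% to 50%, and anywhere from about 1% to about 45% at first-stage tolerability, depending on how DLTs are counted. No single cost figure can be claimed.

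A reader might conclude that 45 mg/QD should not be tested. The documents do not go that far: two of the three HBV-positive responders in the earlier study were treated at 45 mg/QD, and it was the MTD.

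Two limits apply. The Section 4.1 figure is not shown, and the Investigator's Brochure and the schedules of the combination studies were not available.

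**What to change.** **Expansion (Sections 4.1, 4.2, 7.1 and 10.1, carried into the synopsis and 6.4.1).** Let a group expand only if its ORR exceeds 15% and the sponsor medical monitor and investigators document that its starting dose is tolerable. Base that finding on DLTs, dose reductions and discontinuations in all of the roughly 20 dosed subjects.

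**Cycle 1 review (Sections 4.1, 6.2 and 8.2).**

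- First state the DLT window, and whether Grade 3 hyperglycemia controlled by treatment counts.
- Hold one review per group after the first 6 dosed subjects finish or stop Cycle 1. Count every dosed subject, including those who stop for toxicity.
- Review DLTs and dose reductions together, because reductions are the documented problem at 45 mg/QD.
- If 2 or more of the 6 have a DLT, pause that group's new enrollment, non-bindingly, and record the decision: resume, lower the starting dose, or close the group.
- If the chosen definition makes 2 of 6 too sensitive, 4 of 10 is an alternative.

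This is a new within-group rule that borrows the first-stage count; it does not extend the 15-to-30 mg rule.

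**Cost.** Amendment wording and one review per group of data the sponsor already receives. Enrollment need not stop while Cycle 1 data are awaited, no new committee is needed, and N stays at 130. The downside is a possible short review pause in one group, with a probability that depends on the DLT definition chosen.
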